4.4.4 Follow-up Schedule

Patients included in the study will undergo follow-up at one month, six months, twelve months and then annually for five years. In the event of patient death, an autopsy may be performed.

Table 5. Follow-up Table

	Pre- op	Intra- op	Pre- discharge	Month						
				1	6	12	24	36	48	60
CTA/CT Scan with and without	X		X ⁸	X ²						
X-Ray	X ¹			X ¹						
Angiography	X ³	X								
Blood Tests	X ⁴	X ^{5, 6}	X ⁴							
Clinical Exam (including ABI)	X ⁷		X	X ⁷						
Branch Patency ² (duplex ultrasound)				X	X	X	X	X	X	X

- 1 Device X-ray may be requested to provide more focused imaging if potential device integrity issues are identified, but are unable to be confirmed, using CT. Per standard of care: A/P, Lateral and Bilateral oblique views.
- 2 In patients experiencing renal failure during follow-up, duplex ultrasound may be used in conjunction with non-contrast CT.
- 3 Pre-procedure angiography may be requested at discretion of film reviewer.
- 4 Blood tests include hemoglobin and creatinine; PTT and prothrombin collected pre-op and pre- discharge only.
- 5 Blood test for ACT.
- 6 Other intra-op labs for anesthesia.
- 7 Urine pregnancy test (for female patients of childbearing age)
- 8 If deemed necessary by the Principal Investigator

4.4.5 Patient Enrollment and Screening

The investigator will assess potential study subjects with thoracoabdominal aortic aneurysms for their suitability for enrollment into the clinical study. If the patient appears to meet eligibility criteria, either for the primary study arm or the expanded selection arm, then the investigator or clinical study coordinator will discuss the study with the patient and provide patient education materials to adequately inform the patient of potential risks and benefits, required follow-up procedures, and answer any questions. The clinical study coordinator will facilitate the informed consent process. After the patient has been properly consented, the patient will complete additional screening procedures that need to be completed. If the patient does not sign the informed consent, they will not be enrolled in the study. Information to be collected for screening includes:

- Patient demographics
- Medical history
- Current health status
- Physical examination
- Ankle Brachial Index (ABI)
- Pregnancy test (for female patients of childbearing age)

- An X-Ray will be performed per local standard of care. A/P, Lateral and Bilateral Oblique Images will be obtained.
- CTA of the chest, abdomen, and pelvis with 3D reconstruction if renal function allows to evaluate:
 - Access vessels for compatibility with vascular access techniques
 - Obstructive stenting of the visceral vessels
 - Vessel diameters suitable for use with the Valiant™ Thoracoabdominal Stent Graft System
 - Aneurysm rupture
 - Branch stenosis
 - Dissection
 - Patency of left subclavian artery, hypogastric arteries, lumbar arteries, and all four visceral vessels
 - Thrombus or excessive calcification in the neck of the aneurysm
 -
- Complete blood count
- Basic metabolic panel
- For patients with a history of smoking a pulmonary function test
- Cardiac clearance

4.4.5.1 Case Planning

From the pre-op CT, the surgeon will make the following recommended measurements to size the endografts.

1. Length of the proximal seal zone, the distance required to land the thoracic bifurcation stent graft, this requires ≥ 2.5 cm section of healthy aorta, distal to the left subclavian artery.
2. Diameter of the proximal landing zone to define the required diameter of the thoracic bifurcation stent graft. The diameter of the thoracic bifurcation stent graft should be 10-15% larger than the diameter of the aorta to proper oversize the stent graft.
3. Distance from the top of the celiac to the top of the most cephalic renal.
4. Distance from the top of the proximal seal zone to the takeoff of the celiac.
5. Distance from the top of the celiac to the SMA.
6. Angulation at the mid-thoracic aorta.
7. Angulation at the diaphragm.
8. Angulation at the renal arteries.
9. Distance from the right renal to the ipsilateral internal iliac artery.
10. Distance from lower renals to aortic bifurcation.
11. Diameter of the branch vessels (celiac, SMA, left renal, and right renal) to determine the diameter bridging stents needed and percent patency.
12. Diameter of the right and left common iliac to secure the distal seal of the infrarenal bifurcation.
13. Minimum diameter of the access sites (right and left femoral and brachial access site).
14. Length from the access sites to the target treatment zone (right and left femoral and brachial access site).

Note: If treating a dissection under the expanded selection arm the true and false lumen as well as any naturally occurring fenestrations will be evaluated to determine placement of the device and which lumen feeds the branch vessels.

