3.6 Device Description and Drawings

The Visceral Manifold System is made up of two main body components and makes use of several off-the-shelf FDA-approved stent graft components (see Appendix B for system drawing). The two custom main body grafts are the thoracic bifurcation (Figure 1A) and the visceral manifold (Figure 1B). The thoracic bifurcation is deployed in the thoracic aorta and provides the proximal seal for the device. For a Type I or II thoracoabdominal aneurysm the proximal seal is in zone 3, for Type III and V the device seals in zone 4. The two limbs of the thoracic bifurcation allows for continued aortic flow while deploying the visceral segment. The visceral manifold is deployed within the larger 20 mm limb of the thoracic bifurcation to set the stage for the visceral debranching. The branches of the visceral manifold extend to the visceral vessel with the use of covered bridging stents and provide distal seal of the manifold. The smaller 16 mm limb of the thoracic bifurcation extends to the infrarenal segment to either seal in zone 9 for a Type I and V and in zone 10 for Type II, and III. All other connections in the device make use of sizes that are modular and independent of patient anatomy.

Figure 1: Valiant™ Thoracoabdominal Stent Graft System

Aortic components

The thoracic bifurcation stent graft (Medtronic) seals to the native aorta/healthy tissue and bifurcates blood flow in the descending thoracic aorta. The distal end bifurcates into two smaller legs (20 mm and 16 mm) suitable for modular connection to the visceral manifold stent graft and the visceral bypass stent graft. The thoracic bifurcation is composed of a self-expanding, metallic spring scaffold made from nitinol stents sewn to a polyester fabric graft with nonresorbable sutures and is manufactured in the following sizes:

Proximal Diameter (mm)	Target Vessel Diameter Range (mm)	Visceral Perfusion Manifold Diameter (mm)	Visceral Bypass Diameter (mm)	Overall Length (mm)	Catheter Size (Fr)
32	26-29	20	16	118	22
36	30-32			120	25
40	33-36			122	
46	37-42				

Table 1. Thoracic bifurcation dimensions

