The iliac limbs and extenders (Medtronic, Endurant II) will be utilized from a commercially available Endurant II limb or appropriately sized iliac limb extension stent graft. These will be deployed in the infrarenal bifurcation and will provide distal seal of the stent graft system. The iliac limbs will be available in the commercially manufactured sizes and appropriately oversized for implantation in the infrarenal bifurcation.

Principles of Operation

The TAAA Debranching Stent Graft works to bifurcate aortic flow upstream of the target visceral vessels. This bifurcation has a two-fold benefit. First it allows for aortic flow to be compartmentalized into a visceral segment and an infrarenal segment providing for uninterrupted flow to the visceral vessels as well as the infrarenal segment throughout the procedure. If any of the connections cannot be made or the patient status declines during the procedure, then it can be staged and the connections can be made at a later date. Second, the upstream bifurcation encourages more favorable flow conditions in the bridging stents and target vessels which may prevent target vessel occlusion. This is due to the fact that the bifurcations are upstream providing a sweeping transition into the renal arteries that is smooth providing for relatively laminar flow conditions. The design demonstrates that more central aortic flow is obtained with this design increasing flow rates in the visceral vessels to potentially increase target vessel patency (Figure 2).

The device can be used as an off-the-shelf system, negating the need for lead times associated with custom-built devices. The critical sizing that will need to be done is with the proximal end of the thoracic bifurcation, distal landing zone in the aorta or iliac arteries, and the bridging stents. The proximal end of the thoracic bifurcation can be sized by choosing any of the available sizes of the Medtronic TAAA thoracic bifurcation stent grafts, and the sizes of the bridging stents can be manipulated by choosing any of the commercially available sizes of the Atrium iCast. The Atrium iCasts are added to the system in-vivo and connected with passive fixation which negates the need to size the main body components based on the target vessel sizes. All other connections in the device make use of sizes that are the same, independent of patient anatomy.

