4.4.2 Eligibility Criteria

Primary Study Arm

Inclusion Criteria

- A patient may be entered into the study if the patient has at least one of the following:
 - An aneurysm with a maximum diameter of ≥ 5.5 cm or 2 times the normal diameter just proximal to the aneurysm using orthogonal (i.e., perpendicular to the centerline) measurements
 - Aneurysm with a history of growth ≥ 0.5 cm in 6 months
 - Saccular aneurysm deemed at significant risk for rupture
 - Symptomatic aneurysm greater than or equal to 4.5 cm
- Axillary or brachial and iliac or femoral access vessel morphology that is compatible with vascular access techniques, devices or accessories, with or without use of a surgical conduit

- Proximal landing zone for the thoracic bifurcation stent graft that has:
 - ≥ 2.5 cm of nonaneurysmal aortic segment including previously placed graft material (neck) distal to the left subclavian artery (LSA) and a diameter in the range of 26-42 mm
 - Adequate distance from the celiac artery, in order to accommodate cannulation from the antegrade access point when considering the total deployed length of the thoracic bifurcation and visceral manifold
- Iliac artery or aortic distal fixation site, including both native tissue and previously placed graft, greater than or equal to 15 mm in length and diameter in the range of 8 – 25 mm
- Age: ≥ 18 years old
- Life expectancy: > 1 year

Exclusion Criteria

General exclusion

- Patient is a good candidate for and elects for open surgical repair
- Can be treated in accordance with the instructions for use with a legally marketed endovascular prosthesis
- Is eligible for enrollment in a manufacturer-sponsored IDE at the investigational site
- Unwilling to comply with the follow-up schedule
- Inability or refusal to give informed consent

- Urgent or emergent presentation
- Patient is pregnant or breastfeeding
- Patient has a contained rupture
- Patient has a ruptured aneurysm
- Patient has a dissection in the portion of the aorta intended to be treated
- Obstructive stenting of any or all of the visceral vessels
- Poor performance status including two major system failures (including but not limited to cardiovascular, pulmonary, renal, hepatobiliary, and neuromuscular)
- Prior aneurysm repair that would involve relining of the previously placed graft material requiring placement of the investigational system in a landing zone that expands beyond any limits of the previously placed graft material

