4.5.1.3 Performance related risks

There are performance risks of the modular components succumbing to material fatigue resulting in component separation, endoleak or endotension, graft occlusion, kinking, or migration. These risks can be mitigated several ways including adhering to industry standard

seal zone lengths, proper oversizing, lining branch stents with self-expanding stents, regular follow-ups to identify early evidence of migration or separation and allow for appropriate treatment, by the use of completion angiography coupled with cuffs, ballooning, or additional stent grafts if evidence of endoleak.

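### Item 2 of Section 4.4.5.1 asks for 10-15% oversizing of the thoracic bifurcation, but Table 1 assigns grafts that imply 9.5-24.3%

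*Combined protocol and SAP*

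**What the plan says.** Three places in the combined protocol and SAP bear on the diameter of the thoracic bifurcation.

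- **Section 4.4.5.1, Case Planning, item 2.** The surgeon measures the proximal landing zone on the pre-operative CT to choose the graft diameter. The rule given is: "The diameter of the thoracic bifurcation stent graft should be 10-15% larger than the diameter of the aorta to proper oversize the stent graft".
- **Section 3.6, "Table 1. Thoracic bifurcation dimensions".** The table sets the proximal diameter of each graft against a column headed "Target Vessel Diameter Range (mm"). Its first row reads "32 26-29 20 16 118 22": a 32 mm graft for a 26-29 mm aorta. The other rows pair 36 mm with 30-32 mm, 40 mm with 33-36 mm and 46 mm with 37-42 mm. The text of the section then says: "The proximal end of the thoracic bifurcation can be sized by choosing any of the available sizes of the Medtronic TAAA thoracic bifurcation stent grafts". It counts this among the critical sizing steps.
- **Section 4.4.2, Eligibility Criteria.** The landing zone must lie "distal to the left subclavian artery (LSA) and a diameter in the range of 26-42 mm".

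Section 4.5.1.3 lists among its mitigations "seal zone lengths, proper oversizing, lining branch stents with self-expanding stents". Section 4.5.2 adds adherence to the case-planning methods. Neither section gives an oversizing percentage.

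**The concern.** A planner who takes the graft from Table 1 will, at most whole-millimetre diameters, fall outside the percentage in item 2. A planner who starts from item 2 will often find no listed graft that meets it. The documents do not say which takes precedence.

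Item 2 is the only numerical oversizing rule that the protocol states for this component. (The 20-25% in Section 3.3.3.5 concerns flow-diverting stents, a different device.) The thoracic bifurcation provides the proximal seal, and oversizing is a named safeguard against endoleak and migration. Re-intervention for migration or for a Type I or III endoleak counts as failure in the primary effectiveness composite (Section 4.4.3). The instruction that supports this safeguard should agree with the sizes on the shelf.

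**Working it through.** **Inputs.** The graft sizes and target ranges come from Table 1, the 10-15% rule from Section 4.4.5.1 item 2, and the 26-42 mm range from Section 4.4.2. Item 2 expresses the excess relative to the aorta, so

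oversizing = (graft diameter − aortic diameter) / aortic diameter.

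**Step 1: oversizing under Table 1.** For example, (32 − 26)/26 = 23.1% and (46 − 42)/42 = 9.5%.

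| Graft (mm) | Aortic diameter (mm): implied oversizing |
|---|---|
| 32 | 26: 23.1%; 27: 18.5%; **28: 14.3%; 29: 10.3%** |
| 36 | 30: 20.0%; 31: 16.1%; **32: 12.5%** |
| 40 | 33: 21.2%; 34: 17.6%; **35: 14.3%; 36: 11.1%** |
| 46 | 37: 24.3%; 38: 21.1%; 39: 17.9%; **40: 15.0%; 41: 12.2%**; 42: 9.5% |

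Bold entries lie within 10-15%, both limits included. The stated 10-15% is not reproduced: the range is 9.5% to 24.3%. Seven diameters comply (28, 29, 32, 35, 36, 40, 41). Ten do not: 26, 27, 30, 31, 33, 34, 37, 38 and 39 mm are above 15%, and 42 mm is below 10%.

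**Step 2: would another listed size help?** For the nine diameters above 15%, the only candidate is the next smaller graft.

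- 26 and 27 mm: none, since 32 mm is the smallest listed.
- 30 and 31 mm with the 32 mm graft: 6.7% and 3.2%.
- 33 and 34 mm with the 36 mm graft: 9.1% and 5.9%.
- 37, 38 and 39 mm with the 40 mm graft: 8.1%, 5.3% and 2.6%.

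For 42 mm, the 46 mm graft is already the largest. The same ten diameters fail when any of the four grafts may be chosen.

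**Step 3: does the result depend on how the rule is read?**

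- *Rounded to whole percentages:* 42 mm becomes 10% and passes, so 9 of 17 fail.
- *Graft diameter as denominator:* 9 of 17 fail (26, 27, 29, 30, 33, 37, 38, 39, 42).
- *Continuous diameters:* a graft of size G complies for aortas from G/1.15 to G/1.10, which gives 27.83-29.09, 31.30-32.73, 34.78-36.36 and 40.00-41.82 mm. The lengths sum to 1.26 + 1.42 + 1.58 + 1.82, about 6.09 mm of the 16 mm between 26 and 42. That is 38%, so 62% of the range has no compliant graft.

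The count moves by one with the convention. The conflict remains under each.

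**Step 4: is eligibility part of the conflict?** The four target ranges in Table 1 join up to exactly 26-42 mm, so every eligible whole-millimetre diameter has one assigned graft. The eligibility range and Table 1 agree with each other.

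**The case against.** The best case for leaving the text alone is that item 2 is not a limit. It sits in a list of recommended measurements and says *should*. Table 1 gives one graft for every eligible whole-millimetre diameter. At the seven diameters where item 2 can be met, it leads to the same graft as the table, and at no whole-millimetre diameter does it point to a different one. Section 4.4.5.3 also sends the operator to the IFU for deployment and implantation, and the IFU may settle sizing; it is not among the documents.

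Most of this stands. It disposes of several stronger readings that a reader might infer:

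- *That most eligible patients cannot be given a graft.* This would need item 2 to be binding, and its wording does not make it so.
- *That the 26-42 mm criterion is wrong.* It matches Table 1.
- *That 59% of patients are affected.* Ten of 17 gives each millimetre equal weight. The documents give no distribution of landing-zone diameters.
- *That endoleak or migration is itself a component of the primary effectiveness endpoint.* Section 4.4.3 counts the secondary intervention for them; endoleaks appear separately among the secondary endpoints.
- *That oversizing above 15% harms the seal.* No section says so, and nine of the ten mismatches are on that side.
- *That operators or pooled sites will size differently.* This is a single-centre study with one participating investigator named, and the other sites' protocols are not available.

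The objection does not remove the contradiction. Item 2 states its own percentage and does not defer to the IFU. The option in Section 4.4.5.3 to extend proximally with other thoracic grafts changes neither the bifurcation's listed sizes nor item 2. Nor is this an artefact of text extraction: the graft-size and target-range columns are intact in all four rows.

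**Conclusion.** The inconsistency is real and should be corrected. Item 2 gives 10-15%; Table 1 implies 9.5-24.3%. On the literal reading (percentage of aortic diameter, limits included, whole millimetres), 10 of 17 admitted diameters have no listed graft that meets item 2, or 9 of 17 with rounding.

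Its reach is limited. It is a mismatch between a planning sentence and a size table. It does not touch the definition of the 30-day major adverse event endpoint, the performance goal, the sample size or the analysis. It matters because it concerns what is implanted and because the protocol's own risk section relies on the step. The conclusion assumes that the four sizes in Table 1 are the full set available and that nothing in the unseen IFU has been incorporated as an overriding sizing rule.

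**What to change.** Reconcile item 2 of Section 4.4.5.1 with Table 1 in Section 3.6, checking both against the IFU, so that each diameter from 26 to 42 mm has one consistent sizing instruction. If the IFU is meant to govern, item 2 should say so. If the reconciliation alters the target ranges in Table 1, confirm that they still match Section 4.4.2. Which figure is right is for the sponsor and the manufacturer to establish; this review takes no position.

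The cost is a wording amendment. No measurement or procedure is added, because the landing-zone diameter is already taken from the pre-operative CT.

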4.4.5.2 Pre-operative procedures

The patient will be removed from anti-coagulants prior to surgery. The day of surgery the following labs will be taken:

- Complete blood count
- Basic metabolic panel
- Prothrombin time (at physician discretion)
- Partial thromboplastin time (at physician discretion)
- Pregnancy test (for female patients of childbearing age)

The patient will be treated with general anesthesia under standard medical practices along with placement of a lumbar drain when possible.

i. Spinal Drain

- The use of a spinal drain is required for all non-staged procedures on subjects being treated for a Crawford Type I, II, III, or V thoracoabdominal aneurysm
 - In the case of prior spinal surgery or any reason that would put the patient at higher risk for complications, the use is at the physician's discretion
- The use of a spinal drain on staged procedures is at the physician's discretion

The management of anesthesia and the lumbar drain will be performed by the staffed anesthesia team. Standard heparinization practices will be followed and active clotting time will be monitored throughout the procedure. The patient will be prepped in normal sterile fashion from the clavicle to mid-thigh. Additionally contrast will be diluted 50/50 in saline to reduce contrast exposure. Radiation reduction procedures will be followed as allowed.

4.4.5.3 Implant Procedures

Note I: For proximal extension of the thoracic bifurcation, two Valiant Captivia or Valiant Navion thoracic grafts can be used. One to extend the landing zone more proximally and one to layer to prevent wear. Deploy the Valiant Captivia or Valiant Navion thoracic grafts according to their respective manufacturer's IFU and continue according to the implant procedures the Medtronic Valiant Thoracoabdominal Stent Graft System IFU.

Note II: For subjects with advanced iliac atherosclerosis and calcification, we will selectively perform use of open conduits to deliver devices, rather than percutaneous approach. We will selectively perform on table Dyna CT – angiograms at the completion of the case. This will give us a better 3-Dimensional image of the stent and help determine if there is any degree of compression, which can be treated at that time with further stenting.

A. The use of thoracic grafts as a method of staging as a pre-operative adjunct procedure.

a. Thoracic Graft Placement

i. This refers to implanting stent-grafts into the thoracic aorta prior to enrollment into the IDE clinical study.

ii. Device Visualization and Preparation

Refer to the Instructions for use provided for the thoracic components to be used.

iii. Device Placement

Ensure that the distal edge of the thoracic graft is 5-7 cm proximal to the celiac artery.

iv. Thoracic Aorta Component Deployment

Follow the study protocol or IFU for deploying the thoracic graft components.

v. Completion

The date of the index procedure will be targeted for within 6 weeks of the thoracic graft placement, but will be based on physician discretion, clinical presentation, and patient compliance.

B. The implantation of the Valiant™ Thoracoabdominal Stent Graft System is conducted under fluoroscopic/angiographic guidance. Refer to the Valiant™ Thoracoabdominal Stent Graft System (IFU) for techniques and methods for device deployment and implantation.

C. The Valiant Thoracoabdominal Stent Graft System may be implanted in a staged procedure per physician discretion (in either a planned or bail-out fashion). The physician may choose to perform the procedure in two or more stages due to the following conditions/scenarios including but not limited to: hypogastric patency, LSA patency, visceral vessel patency, decreased MEP/SEP potentials, at risk dominant segmental arteries, pulmonary status, or any patient whose

physiologic limitations places them at risk because of the expected length of surgery. The preferred method for planned staging is to create a controlled endoleak which provides limited and temporary perfusion to the aneurysm sac. These methods include but are not limited to placing a bare metal stent in the celiac artery bridge, placing a bare metal stent in the bridge to an alternate visceral artery (ie:SMA or renal), or not completing distal seal in the aorta or iliac arteries.

a. Planned Staged Procedure: Visceral artery bridge endoleak

i. This refers to leaving open a portion of the covered stent bridge between the visceral manifold and target vessel. This is achieved by combining bare metal stents with covered stents to leave ~1-2cm of uncovered conduit along the pathway. This intentional endoleak is resolved in a subsequent intervention where the open portion is covered over by an additional covered stent. It is preferable to achieve this configuration with the bridge to the celiac artery but it can be done in analogous fashion with either the SMA or renal arteries.

ii. Device Visualization and Preparation

Refer to the Instructions for use provided for the bare metal stent for visualization and preparation instruction.

iii. Bridging Stent Deployment

Follow directions in the IFU when deploying bridging stents. Always deploy a covered stent in the leg of the visceral manifold per the VTAAA IFU (9mm iCast at 8atm inflation pressure). When possible, covered stents should be used in the target vessel. The chain of covered stents should be non-continuous in nature with at least one bare metal balloon expandable

stent connecting them. The segment of completely bare stent should be short (~1-2cm) with 2-3cm overlapping with covered stent on either side. Creation of the uncovered segment in as straight a configuration as the anatomy allows will facilitate wire passage during the completion procedure below.

Note: The controlled endoleak should never be created by leaving a visceral manifold limb unconnected to a visceral vessel or with an uncovered segment >2cm due to the pressurization of the aneurysm sac. If a visceral vessel is occluded, the corresponding visceral manifold limb should be plugged with a vascular plug and an alternative (patent) vessel utilized for the staging procedure. The placement of the non-continuous chain of covered bringing stents and a bare metal stent helps direct flow while creating a controlled endoleak.

iv. Completion

Completion of the staged procedure is targeted for 4-6 weeks following the index procedure, but will be based on physician discretion, clinical presentation, and patient compliance.

Note: The physician may choose to complete the procedure earlier if the patient is symptomatic or has other concerns for aneurysm sac growth or rupture.

Completion procedure may be performed under local or general anesthesia. Vascular access will be established in the brachial or axillary

artery. The staged limb of the visceral manifold will be cannulated and the bare segment will be covered over by at least one iCast.

b. Planned Stage Procedure: Delayed distal seal

i. This refers to completing the visceral debranching (manifold to target arteries) with covered stents and subsequently leaving out one or more of the distal aortic/iliac components.

ii. Device Visualization and Preparation

Refer to the Instructions for use provided for the distal aortic/iliac components to be used.

iii. Distal Aortic/Iliac Component Deployment

Follow the study protocol or IFU for deploying the distal aortic/iliac components.

iv. Completion

Completion of the staged procedure is targeted for 4-6 weeks following the index procedure, but will be based on physician discretion, clinical presentation, and patient compliance.

Note: The physician may choose to complete the procedure earlier if the patient is symptomatic or has other concerns for aneurysm sac growth or rupture.

Completion procedure may be performed under local or general anesthesia.

c. Bail-out Stage Procedure

- i. A bail-out method may be used for staging in the event patient status declines during the case or inability to technically complete the case.
- ii. Device Visualization and Preparation
Refer to the Instructions for use provided for the components to be used.
- iii. Device Deployment
Refer to the Valiant™ Thoracoabdominal Stent Graft System (IFU) for device deployment and implantation of the remaining components.
- iv. Completion due to patient status decline
Completion of a bail-out staged procedure due to patient status should be completed as soon as clinically feasible following the index procedure, but will be based on physician discretion, clinical presentation, and patient compliance.
- Note: The physician may choose to delay staging if the patient has complications or there are concerns with completing the secondary procedure.*
- v. Completion due to inability to technically complete the case
Completion of a bail-out procedure due to technical challenges have the following options that present no more risk than the alternative of no treatment.
 - a. Complete case at another date
 - b. Medical management
 - c. Convert to open surgical repair

- d. Referral to another facility/investigator that can complete the procedure

Note: Caution should be taken when relining previously placed graft material to prevent complications from graft on graft friction including decreased graft maneuverability and challenges repositioning.

Note: For proximal extension of the thoracic bifurcation, two Valiant Captivia or Valiant Navion thoracic grafts can be used. One to extend the landing zone more proximally and one to layer to prevent wear. Deploy the Valiant Captivia or Valiant Navion thoracic grafts according to their respective manufacturer's IFU and continue according to the implant procedures the Medtronic Valiant Thoracoabdominal Stent Graft System IFU.

Note: For type 1 and 5 aneurysms the distal end of visceral bypass (VB) should be sized to provide the distal seal with the aorta and then proceed to Step 4.4.5.5, Completion Procedures. For type 2 and 3 proceed to deployment of the infrarenal bifurcation and Endurant II limb stent graft instructions in the Medtronic TAAA Debranching Stent Graft System IFU.

Note: If the VB is too short or too small to provide distal seal, a Valiant Captivia stent graft or Endurant Limb may be used in place or in conjunction with the Visceral Bypass to provide adequate distal seal. For type 2 and 3 proceed to deployment of the infrarenal bifurcation and Endurant II limb stent graft instructions in the Medtronic TAAA Debranching Stent Graft System IFU. If a commercially available Endurant limb or Valiant stent graft is used as the Visceral Bypass a commercially available Endurant

mainbody stent graft with suprarenal fixation and a Gore cuff is required for adequate fixation. See Step 1.4.5.5.3.C and Step 1.4.5.5.4.D. below for deployment procedures.

Note: If treating a subject with an occluded visceral vessel, a vascular plug may be used to occlude the extra limb of the TAAA Visceral Manifold stent graft.

B. Surgical Decision Pathway and Bailouts

[figure not shown]

Figure 4: Surgical decision path and possible bailouts

C. Visceral Bypass (VB) Instructions (Endurant Long Limb)

1. Insert a guidewire from the groin through the 16-mm limb of the thoracic bifurcation.
2. Refer to the manufacturer's IFU (Endurant) for visualization and preparation instructions.

3. The proximal radiopaque marker of the VB stent graft should be aligned with the bifurcation of the thoracic bifurcation.
4. Verify there is a 5 cm overlap with the 16 mm leg of the thoracic bifurcation.
5. Deploy the VB according to the manufacturer's IFU (Endurant).
6. Leave the guidewire in place and remove the delivery system according to the manufacturer's IFU (Endurant).

D. Infrarenal Bifurcation (IB) Instructions (Endurant Mainbody)

1. Refer to the manufacturer's IFU (Endurant) for visualization and preparation instructions.
2. Identify the guidewire that passes through the VB stent graft.
3. From the ipsilateral groin access point, insert the delivery system over the guidewire.
4. Slowly advance the bifurcated graft into the VB stent graft.
5. Verify there is a 4-5cm overlap with the VB stent graft.
6. Confirm the distal portion of the contralateral leg is above the aortic bifurcation.
7. Confirm the radiopaque ring marker on the distal end of the contralateral leg is in a position to allow for cannulation from the contralateral iliac artery.
8. Confirm the distal target landing zone relative to anatomical landmarks (i.e. internal iliac artery).
9. Deploy the bifurcated graft according to the manufacturer's IFU (Endurant).
10. Release the tip capture mechanism according to the manufacturer's IFU (Endurant).
11. Remove the delivery system according to the manufacturer's IFU (Endurant).
12. Complete distal seal of the bifurcated graft into the common iliacs according to the manufacturer's IFU (Endurant).

13. If the Endurant mainbody with suprarenal fixation is used deploy a Gore Aortic Extender Endoprostheses according to the manufacturer's IFU (Gore Excluder) over the suprarenal fixation stent of the bifurcated graft (Endurant mainbody) to seal and prevent endoleaks in the event the suprarenal fixation stent were to puncture the graft material.

